1.1. Synopsis

Protocol Title: A Phase 2 Randomized, Double-Blind, Placebo-Controlled, Parallel-Group Study of the Safety and Efficacy of NG101 Administered Orally to Patients with Gastroparesis

Rationale:

The purpose of this study is to evaluate the safety and efficacy of NG101 when administered orally across a range of doses to participants aged 18 years or older with diabetic or idiopathic gastroparesis. Results of this study will guide optimal dose selection for phase 3.

Objectives and Endpoints

Objectives	Endpoints
Primary	

 To determine the efficacy of NG101 to reduce nausea severity in participants with gastroparesis To evaluate the safety of NG101 in participants with gastroparesis 	
 Change from baseline at Weeks 7 through 12 in the nausea severity score in the Diabetic and Idiopathic Gastroparesis Symptoms daily diary (DIGS-DD). Incidence and severity of treatment-emergent adverse events (TEAEs), treatment-emergent adverse events of special interest (TEAESIs), and treatment-emergent serious adverse events (TESAEs); evaluation of safety laboratory assessments, vital signs, electrocardiogram (ECG) results, and physical examination findings.

 To determine the efficacy of NG101 to: 
 Reduce the frequency and severity of vomiting Reduce the symptom severity of early satiety, post-prandial fullness, and abdominal pain Reduce the duration of nausea Reduce the duration of abdominal pain Reduce the overall severity of signs and symptoms of gastroparesis Reduce the use of rescue medication 	
Key Secondary Endpoints
 
 Change from baseline at Weeks 7 through 12 in the DIGS-DD: 
 Number of discrete episodes of vomiting Early satiety severity score Post-prandial fullness severity score Abdominal pain severity score Total severity score (nausea, early satiety, post-prandial fullness, abdominal pain)


 • To evaluate the pharmacokinetics (PK) of NG101 • To evaluate the pharmacodynamic (PD) effects of NG101 	
Additional Secondary Endpoints
 
 • Change from baseline at Weeks 7 through 12 in the: 
 ◦ Number of hours of nausea per 24-hour period ◦ Number of hours of abdominal pain per 24-hour period • Change from baseline at Weeks 7 through 12 in the vomiting severity score • Percent of nausea-free days • Patient Global Impression of Severity (PGI-S) score • Patient Global Impression of Change (PGI-C) score • Change from baseline to Week 12 in: 
 ◦ Patient Assessment of Upper Gastrointestinal Disorders (PAGI)-Symptoms (SYM) ◦ PAGI- quality of life (QOL) ◦ Total and subscale scores on the Nausea Profile (NP) • Change from baseline through Week 4 in each of the components of the DIGS-DD (nausea, vomiting, early satiety, post-prandial fullness, and abdominal pain) • Change from baseline in gastroparesis symptoms as measured by the Gastroparesis Cardinal Symptom Index daily diary (GCSI-DD) • Change from baseline in weekly Treatment Satisfaction score • Weekly use of rescue medication • PK parameters • Prolactin levels at indicated timepoints

Exploratory Objectives
 
 • To evaluate the efficacy of NG101 to reduce the symptom severity of feeling of abdominal fullness and abdominal bloating • To evaluate the efficacy of NG101 to improve the symptom of nausea 	
 • Change from baseline at Weeks 7 through 12 in the feeling of abdominal fullness severity score and in the abdominal bloating severity score • Level of improvement reported on the Nausea Improvement assessment


 • Association of exposure and clinical response • Additional analyses of clinical response in gastroparesis symptoms • Healthcare resource utilization • Association of serum glucose with clinical response 	
 • Association of PK parameters and changes in gastroparesis symptom PRO scores. • Association of PK parameters and safety assessments • Achievement of threshold levels of improvement or worsening in each of the components of the DIGS-DD (nausea, vomiting, early satiety, post-prandial fullness, and abdominal pain) • Composite symptom severity scores • Number of visits to healthcare providers • Association of serum glucose levels and HgbA1c with gastroparesis symptom PRO scores
---	---

Abbreviations: DIGS-DD = Diabetic and Idiopathic Gastroparesis Symptoms Daily Diary; ECG = electrocardiogram; GCSI-DD = Gastroparesis Cardinal Symptom Index Daily Diary; PAGI-SYM = Patient Assessment of Upper Gastrointestinal Disorders -Symptoms Questionnaire; PAGI-QOL = Patient Assessment of Upper Gastrointestinal Disorders -Quality of Life; PGI-C = Patient Global Impression of Change; PGI-S = Patient Global Impression of Severity; PD = pharmacodynamic; PK = pharmacokinetic; PRO = patient-reported outcomes; TEAEs = treatment-emergent adverse events; TEAESIs = treatment-emergent adverse events of special interest; TESAEs = treatment-emergent serious adverse events.

Overall Design

This is a randomized, double-blind, parallel-group (4 arms), placebo-controlled, multicenter study to evaluate the safety and efficacy of 3 dose levels of NG101 compared with placebo in participants with diabetic or idiopathic gastroparesis.

Following a Screening Period of up to 4-weeks, eligible participants will enter a 2-week Pretreatment Period, during which time they will complete specified gastroparesis symptom assessments to establish baseline data and to determine compliance with completion of these assessments. Following completion of the Pretreatment Period, a participant's randomization eligibility will be determined (based on all inclusion/exclusion criteria, including the participant's compliance with eDiary completion).

Participants who do not initially meet study screening criteria (ie, are screen failures) may be rescreened (no more than 1 additional screening) after consultation with and approval by the sponsor. A participant's eligibility for the study must be confirmed by the sponsor's Medical Monitor, or designee, prior to randomization.

Participants eligible for the clinical study will be randomized in a 1:1:1:1 ratio to receive either NG101 treatment arms of 5 mg, 10 mg, or 20 mg, or matching placebo during a 12-week Treatment Period. Randomization will be stratified on the following factors: gastroparesis etiology (diabetes vs idiopathic), sex (male vs female), and cannabinoid use (yes vs no). Determination of diabetes etiology will be done according to the medical history data at Screening.

Two weeks following the Week 12 Visit, participants will return to the clinic for an End of Study (EoS) Visit / Follow-up Visit.

If a participant permanently discontinues study medication (for any reason) prior to the Week 12 Visit, the participant must attend the Early Discontinuation Visit as soon as possible, and then the Safety Follow-up Visit 2 weeks later.

Study Assessments:

Study assessments will be performed at the times specified in the Schedule of Activities (SoA – see [Section 1.3](#)).

The primary efficacy objective is to determine the efficacy of NG101 to reduce nausea severity in participants with gastroparesis. The primary endpoint is the change from baseline at Weeks 7 through 12 for the nausea severity score in the Diabetic and Idiopathic Gastroparesis Symptoms Daily Diary (DIGS-DD). Key secondary efficacy endpoints will also be assessed by the DIGS-DD and include changes from baseline at Weeks 7 through 12 in the DIGS-DD number of discrete episodes of vomiting, early satiety severity score, post-prandial fullness severity score, abdominal pain severity score, and total severity score (nausea, early satiety, post-prandial fullness, abdominal pain). An eDiary will be used to collect information for the primary and key secondary endpoints.

In addition, blood samples will be obtained from all participants to measure plasma levels of metopimazine and metopimazine acid following single-dose administration (Day 1) and at steady-state after multiple-dose administration (Week 2). Blood samples for PK will be collected at the Day 1 and Week 2 visits for all participants (up to 3 hours after the first dose on each occasion). In a subset of participants (8 to 10 participants per treatment arm; 32 to 40 participants total), intensive sampling will be performed (up to 6 hours after the first dose at the Day 1 and Week 2 visits, as well as 1 and 2 hours after the second dose at the Day 1 visit).

Disclosure Statement:

This is a parallel group treatment study with 4 arms that is participant, investigator, and sponsor blinded.

Number of Participants:

A total of approximately 280 participants will be randomized to achieve an estimated 224 participants completing the 12-week Treatment Period (and approximately 56 participants per treatment arm). At least 120 randomized participants will have diabetic gastroparesis and at least 120 randomized participants will have idiopathic gastroparesis. Up to approximately 140 participants can be cannabinoid users, and of these, up to approximately 56 can be marijuana users.

Intervention Groups and Duration:

The total duration of the study for each participant will be approximately 20 weeks.

On Day 1 of the Treatment Period, eligible participants will be randomized in a 1:1:1:1 ratio to receive either NG101 5 mg, 10 mg, or 20 mg, or matching placebo. Study drug will be administered orally 4 times per day (QID) for 12 weeks. The 20 mg arm will initiate dosing on

Day 1 with 5 mg QID for 4 days, followed by 10 mg QID for 3 days, and then 20 mg QID through Week 12. No titration will occur in the 5 mg and 10 mg arms.

[figure not shown]
The study drug should be taken by participants approximately 30 minutes before a meal 3 times a day and 30 minutes before bedtime, with a minimum interval of 4 hours between doses.

Data Monitoring Committee and Data Safety Monitoring Board:

A Data Monitoring Committee (DMC) comprised of representatives from the sponsor and CRO will review blinded data on an ongoing basis.

An unblinded independent safety review conducted by a Data Safety Monitoring Board (DSMB) will be triggered if any of the following conditions are met: 3 or more participants in the study exhibit extrapyramidal symptoms (EPS); 1 or more participants have neuroleptic malignant syndrome (NMS); 3 or more participants are discontinued due to orthostatic hypotension-related adverse events (AEs); other events considered of high clinical significance by the sponsor are observed. The DSMB will then make any recommendations to the sponsor regarding conduct of the study.

1.2. Schema

Primary endpoint: Change from baseline in the nausea severity score in the Diabetic and Idiopathic Gastroparesis Symptoms daily diary (DIGS-DD)

★ Clinic visit

* The 20 mg arm will initiate dosing with 5 mg QID for 4 days, followed by 10 mg QID for 3 days, and then (starting on Day 8) 20 mg QID

1.3. Schedule of Activities (SoA)

Procedure	Screening Visit	Pre-treatment Visit	Treatment Period Visits						E/D Visit	EoS / Follow-up Visit	Notes	
	(up to 28 days before Day -14)	Day	Day	Week								
		-17 to -14	1	(± 2d)	2	(± 2d)	4	(± 2d)	8	(± 3d)	12	(± 3d)
Informed consent	X											
Inclusion and exclusion criteria	X		X									Recheck clinical status / check compliance before randomization on Day 1
Demography	X											
Medical history	X											Including prior treatments for gastroparesis (dose, regimen, duration), substance use and, for females, menstrual history
Gastric emptying test	X											FDA-approved breath test completed and assessed for eligibility in participants who have not completed the breath test or scintigraphy test within 12 months prior to Screening, or during the Screening Period. Must be a minimum of 7 days between the gastric emptying study and the start of the Pretreatment Period.

Procedure	Screening Visit	Pre-treatment Visit	Treatment Period Visits						E/D Visit	EoS / Follow-up Visit (14 ± 3 days after last dose)	Notes	
	(up to 28 days before Day -14)	Day	Day	Week								
		-17 to -14	1	(± 2d)	2	(± 2d)	4	(± 2d)	8	(± 3d)	12	(± 3d)
Physical examination	X		X				X	X	X	X	X	A physical exam including neurologic, cardiovascular, pulmonary, abdominal and breast exams will be performed at Screening, Day 1, and Weeks 4, 8, and 12 (or E/D) as well as at the Follow-up Visit. Height will be measured on Day 1. For females, menstrual cycle will be recorded during the study.
Weight	X	X	X	X	X	X	X	X	X	X	X	
Vital signs	X	X	X	X	X	X	X	X	X	X	X	Vital signs include oral temperature, pulse rate, respiratory rate, and blood pressure. Orthostatic vital signs will also be checked at Screening, and at the Day 1, Week 1, and Week 2 visits. See Section 8.4.2 .

Procedure	Screening Visit	Pre-treatment Visit	Treatment Period Visits						E/D Visit	EoS / Follow-up Visit (14 ± 3 days after last dose)	Notes	
	(up to 28 days before Day -14)	Day	Day	Week								
		-17 to -14	1	(± 2d)	2	(± 2d)	4	(± 2d)	8	(± 3d)	12	(± 3d)
12-lead ECG	X		X		X			X	X	X		On Day 1 and Week 2, ECGs will be performed in triplicate at the time of PK sampling (ie, predose and at 1 [near anticipated T_{max}], 2, and 3 hours postdose). For the Intensive PK subset, in addition to the ECG assessments described above, triplicate ECGs should be taken at hour 6 (on Day 1 and Week 2) as well as 1 and 2 hours after the second dose at the Day 1 visit. See Section 8.4.3 .
HIV, Hepatitis B and C screening	X											
Thyroid stimulating hormone (TSH)	X											If TSH is above the upper limit of normal, then free T4 will be checked
Estimated glomerular filtration rate (eGFR)	X											eGFR will be calculated using Chronic Kidney Disease Epidemiology Collaboration [CKD-EPI] equation. See Appendix 10.7 .
Serum pregnancy test (WOCBP only)	X											
Testosterone (males only)	X											If testosterone is below the lower limit of normal, the participant is excluded.

Procedure	Screening Visit	Pre-treatment Visit	Treatment Period Visits						E/D Visit	EoS / Follow-up Visit (14 ± 3 days after last dose)	Notes	
	(up to 28 days before Day -14)	Day	Day	Week								
		-17 to -14	1	(± 2d)	2	(± 2d)	4	(± 2d)	8	(± 3d)	12	(± 3d)
Urine pregnancy test (WOCBP only)			X				X	X	X	X	X	
Urine sample for drug test	X								X	X		
Blood and urine sample for safety laboratory assessments	X		X	X	X	X	X	X	X	X	Hematology and Serum Chemistry – see Appendix 10.3 . Blood samples should be drawn prior to dosing on Day 1 and Week 2.	
Serum prolactin	X		X		X				X	X	X	Blood samples for prolactin will be drawn at Screening, prior to dosing on Day 1, Week 2 and Week 12, as well as 1-hour after dosing. For the Intensive PK subset, in addition to the samples described above, blood samples will also be drawn 2, 3 and 6 hours after dosing on Day 1 and Week 2. One sample will also be taken at the EoS / Follow-up visit for all participants. See Section 8.8., Table 5
HgbA1c	X		X					X	X			
Blood sample for genetic testing (optional)			X								Where permitted and in participants who consent.	
Randomization			X									

Procedure	Screening Visit	Pre-treatment Visit	Treatment Period Visits						E/D Visit	EoS / Follow-up Visit (14 ± 3 days after last dose)	Notes						
	(up to 28 days before Day -14)	Day	Day	Week													
		-17 to -14	1	2 (± 2d)	4 (± 2d)	8 (± 3d)	12 (± 3d)										
Dispense study drug			X	X	X	X	X				Compliance with study drug use will be assessed at each visit.						
Dispense rescue medication			X	X	X	X	X				Compliance with rescue medication use will be assessed at each visit.						
Study medication											
4 × per day (QID) The study drug should be taken approximately 30 minutes before a meal 3 times a day and 30 minutes before bedtime, with a minimum interval of 4 hours between doses.
 
Day 1: first dose in clinic, and second dose in clinic for Intense PK subset
 
Week 1: a dose in clinic
 
Week 2: first dose of the day in clinic
 
Week 12: a dose in clinic
 
See Section 6.1.
						
Healthcare resource utilization											See Section 8.12 .						
AE / SAE review											See Section 8.5 .						
Concomitant medication review											Including cannabinoid use						

Procedure	Screening Visit	Pre-treatment Visit	Treatment Period Visits						E/D Visit	EoS / Follow-up Visit	Notes	
	(up to 28 days before Day -14)	Day	Day	Week				-17 to -14	(14 ± 3 days after last dose)			
		1 (± 2d)	2 (± 2d)	4 (± 2d)	8 (± 3d)	12 (± 3d)						
DIGS-DD and Gastroparesis additional daily assessments											Completed once daily at the same time each day. Compliance with completion of the daily diary will be assessed at each visit.	
PGI-S, PGI-C and Treatment Satisfaction Assessment											Completed once weekly on the 7 th day of the week. PGI-C and Treatment Satisfaction will be completed after Day 1	
GCSI-DD assessment		X						X*			The GCSI-DD is completed once daily during the Pretreatment Period, and *daily during the last week of the Treatment Period (participant will receive the GCSI-DD beginning the day after completing the Week 11 PRO's).	
PAGI-SYM, PAGI-QOL, Nausea Profile,			X		X	X	X	X	X	X	At relevant visits, these assessments should be completed first before any other assessments/examinations are completed.	
Nausea Improvement Assessment								X	X		Completed once at the end of the study.	

Procedure	Screening Visit	Pre-treatment Visit	Treatment Period Visits						E/D Visit	EoS / Follow-up Visit (14 ± 3 days after last dose)	Notes	
	(up to 28 days before Day -14)	Day	Day	Week								
		-17 to -14	1	(± 2d)	2	(± 2d)	4	(± 2d)	8	(± 3d)	12	(± 3d)
Blood sample(s) for plasma drug concentration			X		X							

Abbreviations: AE = adverse event; ECG = electrocardiogram; E/D = early discontinuation; eGFR = estimated glomerular filtration rate; EoS = end of study; FDA = Food and Drug Administration; GCSI-DD = Gastroparesis Cardinal Symptom Index – Daily Diary; HIV = human immunodeficiency virus; PAGI-QOL = patient assessment of upper gastrointestinal disorders-quality of life; PAGI-SYM = patient assessment of upper gastrointestinal disorders-symptom severity index; PGI-C = Patient Global Impression of Change; PGI-S = Patient Global Impression of Severity; PK = pharmacokinetic(s); PRO = patient-reported outcome(s); QID = four times per day; SAE = serious adverse event; TSH = thyroid stimulating hormone; WOCBP = women of child-bearing potential.

2. Introduction

NG101 is a potent and selective, peripherally-restricted (ie, very limited ability to penetrate the brain), human Ether-à-go-go-related gene (hERG) negative (ie, no hERG inhibition at expected human plasma exposures), dopamine D₂/D₃ receptor antagonist being evaluated for the treatment of gastroparesis. It is also an antagonist with lower affinity for dopamine D₁, adrenergic alpha-1, histamine H₁, and serotonin 5-HT_{2A}/5-HT_{2B} receptors.

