4.2. Scientific Rationale for Study Design

Patients with gastroparesis arising from either diabetic or idiopathic etiology will be enrolled in this study. Both subsets of patients may derive improvement in symptoms from D₂ inhibition, and thus treatment with metopimazine. Documentation of delayed gastric emptying is required in order to confirm the diagnosis of gastroparesis. A minimum severity of symptoms is required in order to facilitate demonstration of study drug treatment effect. The 12-week duration of the Treatment Period will enable assessment of the durability of response to treatment with metopimazine.

Dose selection for this study is based on the evaluation of a range of estimated target receptor (D₂) occupancies, phase 1 study results, and the clinical experience with marketed metopimazine in France (see [Section 4.3](#)). The dose escalation in the 20 mg QID treatment arm is included as mitigation against potential OH AEs, and to assess adaptation to alpha-1 receptor inhibition.

The primary endpoint of this study is the change in nausea severity. This endpoint was chosen since nausea is one of the most frequently reported symptoms of gastroparesis, and also has a major impact on patient quality of life ([FDA 2019](#)). Moreover, nausea is likely to be the most sensitive symptom of gastroparesis to facilitate detection of a treatment effect from D₂ inhibition.

A novel PRO tool to assess the signs and symptoms of gastroparesis, the DIGS-DD, is being developed and employed in this study since no qualified assessment tools for gastroparesis currently exist. The DIGS-DD will assess the impact of NG101 on the symptoms of gastroparesis in this study, and results will enable a determination of appropriateness and reliability of the DIGS-DD for use in future potentially pivotal studies.

Rescue medication rules have been designed to balance the need to treat a participant's symptoms and the ability to detect a treatment effect of metopimazine. Stratification factors were identified as potentially impacting the clinical course and/or treatment response, and have been incorporated into planned analyses.

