8.4.2. Vital Signs

Vital signs, including oral temperature, pulse rate, respiratory rate, and BP will be measured at each study visit while the participant is in the sitting position. A standardized oscillometric automated BP device will be used; manual auscultatory assessment will be used only if the BP reading cannot be captured by the standardized automated device (eg, based on specific physiologic condition, or if the automated device is not functional). Blood pressure and pulse measurements should be preceded by at least 5 minutes of rest for the participant in a quiet setting without distractions (eg, television, cell phones). Additional information regarding the standardized automated office BP assessment will be outlined in the training manual provided by the cardiac safety laboratory.

Orthostatic vital signs will be assessed as follows (and as clinically indicated; see also the SoA in [Section 1.3](#)).

- At Screening, BP and heart rate will be measured while sitting and after 1 minute in the standing position.
- At the Day 1 Visit, BP and heart rate will be measured before dosing and at 1, 2, and 3 hours after dosing. Measurements will be done while the participant is sitting, as well as after 1 minute in the standing position.
- At the Week 1 Visit, BP and heart rate should be measured before dosing and at 1 hour after dosing. Measurements will be done while the participant is sitting, as well as after 1 minute in the standing position.
- At the Week 2 visit, BP and heart rate will be measured before dosing, and at 1, 2, and 3 hours after dosing. Measurements will be done while the participant is sitting, as well as after 1 minute in the standing position.

For participants in the Intensive PK subset, in addition to the assessments described above, orthostatic vital signs will also be assessed at the Day 1 and Week 2 visits at hours 4, 5, and 6, as well as 1 and 2 hours after the second dose in the clinic on Day 1.

8.4.3. *Electrocardiograms*

TriPLICATE 12-lead ECGs will be obtained as outlined in the SoA (see [Section 1.3](#)) using an ECG machine that automatically calculates the heart rate and measures PR, QRS, QT, and QTcF intervals.

At each time point at which triplicate ECG are required, 3 individual ECG tracings should be obtained as closely as possible in succession, but no more than 2 minutes apart. The full set of triplicates should be completed in less than 4 minutes.

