8.8. Pharmacodynamics

Inhibition of dopamine receptors is associated with an increase in serum prolactin levels. This is because dopamine has an inhibitory effect on the anterior pituitary lactotrophs which secrete prolactin. Thus, prolactin levels will be measured in this study (as indicated in [Table 5](#)) to characterize the pharmacodynamic effects of NG101. Blood samples for serum prolactin assessment will be sent to the central laboratory [REDACTED]. Results of prolactin level measurements after the pre-dose assessment on Day 1 will remain blinded until database lock.

Note that during the following visits, study drug will be administered in the clinic:

- **Day 1:** first dose in the clinic, and second dose of the day in the clinic for those participants in the Intense PK subset
- **Week 1:** a dose in the clinic (ie, not necessarily the first dose of the day)
- **Week 2:** first dose of the day in the clinic
- **Week 12:** a dose in the clinic (ie, not necessarily the first dose of the day)

Table 5: Serum Prolactin Sampling Times

Study Day	All Participants (\pm Time window)	Intensive PK Subset (\pm Time window)
Screening Visit	Screening Visit	Screening Visit
Day 1	Predose ^a 1 hour (\pm 5 minutes) -- -- --	Predose ^a 1 hour (\pm 5 minutes) 2 hours (\pm 5 minutes) 3 hours (\pm 10 minutes) 6 hours (\pm 10 minutes)
Week 2 Visit	Predose ^a 1 hour (\pm 5 minutes) -- -- --	Predose ^a 1 hour (\pm 5 minutes) 2 hours (\pm 10 minutes) 3 hours (\pm 10 minutes) 6 hours (\pm 10 minutes)
Week 12 or E/D Visit	Predose ^a 1 hour (\pm 5 minutes)	Predose ^a 1 hour (\pm 5 minutes)
EoS / Follow-up Visit	EoS / Follow-up Visit	EoS / Follow-up Visit

Abbreviations: E/D = Early discontinuation; EoS = End of study; PK = pharmacokinetic

^a Within 15 to 20 minutes before dosing.

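### No orthostatic measurement is scheduled after Week 2, so for about 90% of the time at 20 mg an orthostatic effect can be seen only through symptoms, adverse event reports or unscheduled checks

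*Combined protocol and SAP*

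**What the plan says.** The vital-signs note in the Schedule of Activities (Section 1.3) reads: "Orthostatic vital signs will also be checked at Screening, and at the Day 1, Week 1, and Week 2 visits". Section 8.4.2 gives the times:

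- "At the Day 1 Visit, BP and heart rate will be measured before dosing and at 1, 2, and 3 hours after dosing".
- "At the Week 1 Visit, BP and heart rate should be measured before dosing and at 1 hour after dosing".
- "At the Week 2 visit, BP and heart rate will be measured before dosing, and at 1, 2, and 3 hours after dosing".

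Each measurement is taken sitting and again after 1 minute standing. The Intensive PK subset has further readings on Day 1 and at Week 2. The list is introduced with "Orthostatic vital signs will be assessed as follows (and as clinically indicated"), so unscheduled checks are allowed. Routine vital signs "will be measured at each study visit while the participant is in the sitting position", which cannot show a postural fall.

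Section 4.2 says that the dose escalation in the 20 mg arm "is included as mitigation against potential OH AEs, and to assess adaptation to alpha-1 receptor inhibition". The schema in Section 1.2 has that arm reach 20 mg on Day 8, after 4 days on 5 mg and 3 days on 10 mg.

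At Week 12, participants take "a dose in the clinic (ie, not necessarily the first dose of the day"), and Table 5 in Section 8.8 schedules prolactin samples before that dose and 1 hour after it. No standing reading goes with them. Section 9.3.6 plans descriptive summaries of vital signs and names no orthostatic or adaptation summary.

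**The concern.** Assessing adaptation means asking whether the orthostatic response to a given exposure becomes smaller with continued dosing. That takes comparable readings at more than one time, preferably at the same dose. In the arm where the question matters most, only one scheduled orthostatic visit is certain to be at the target dose, and it comes early in 12 weeks of treatment.

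Section 4.3 describes orthostatic change as the one safety trend in phase 1 and as dose-dependent, and Section 2.3 says that this trial will guide the phase 3 dose. If few orthostatic problems are reported after Week 2, the data will not separate true adaptation from falls in blood pressure that were not measured because they caused no complaint. The orthostatic hypotension AESI in Table 3 needs a measured fall as well as severe postural symptoms. After Week 2, therefore, even confirming an AESI depends on someone taking an unscheduled reading.

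**Working it through.** The plan gives no figure of its own on this point, so the check is a count of readings and days.

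**Inputs.** Treatment lasts 12 weeks, or 84 days (Section 1.1). The 20 mg dose starts on Day 8 (Section 1.2). The Week 1 and Week 2 windows are read as ±2 days and the Week 12 window as ±3 days (Section 1.3). Reading times are from Section 8.4.2. The sections used here do not say whether Week k means Day 7k or Day 7k + 1, so both are shown.

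**Scheduled post-dose orthostatic readings per participant, outside the Intensive PK subset**

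| Visit | Readings | Dose in the 20 mg arm |
|---|---|---|
| Day 1 | 3 (1, 2, 3 h) | 5 mg |
| Week 1 | 1 (1 h) | 10 mg or 20 mg |
| Week 2 | 3 (1, 2, 3 h) | 20 mg |
| Weeks 4, 8, 12 | 0 | 20 mg |

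In the Intensive PK subset the counts are 3 + 3 + 2 = 8 on Day 1 and 3 + 3 = 6 at Week 2, and again none later.

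**Timing against the start of 20 mg (visit day minus 8)**

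- Week 1: Day 7 or 8, with window Day 5 to 10. That is 3 days before to 2 days after the first 20 mg day. Days 5 to 7 are on 10 mg and Days 8 to 10 on 20 mg.
- Week 2: Day 14 or 15, with window Day 12 to 17. That is 6 to 7 days after the start of 20 mg nominally, and 4 to 9 days across the window.
- Week 12: Day 84 or 85, with window Day 81 to 88. That is 73 to 80 days after the start of 20 mg.

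**Time at 20 mg after the last scheduled reading**

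- Days at 20 mg: 84 − 7 = 77.
- Week 2 on Day 14: 84 − 14 = 70, and 70/77 = 90.9%.
- Week 2 on Day 15: 84 − 15 = 69, and 69/77 = 89.6%.
- Window limits: Day 12 gives 72/77 = 93.5%; Day 17 gives 67/77 = 87.0%.

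**Why comparisons over time should use one common reading.** Suppose that each reading has the same chance p of showing a fall, independently, in 70 participants. The expected number with at least one fall at a visit with m readings is 70 × (1 − (1 − p)^m). These values of p are assumptions for illustration only.

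| p | Day 1 (m = 3) | Week 1 (m = 1) | Week 2 (m = 3) |
|---|---|---|---|
| 2% | 4.1 | 1.4 | 4.1 |
| 5% | 10.0 | 3.5 | 10.0 |
| 10% | 19.0 | 7.0 | 19.0 |

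With no change in the true effect, a count of participants with any fall dips at Week 1 and recovers at Week 2. The 1-hour reading is the only post-dose time common to all three visits.

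**The case against.** The early focus is a reasoned choice. Section 4.3 reports that phase 1 orthostatic hypotension at 15 and 30 mg was confined to the first day and the first hour. Recurrence over several days was seen at 45 mg every 6 hours, above any dose used here (Section 2.2.1.1). Surveillance also continues after Week 2. Adverse events are collected to the Follow-up Visit (Section 8.5.1), and orthostatic readings may be taken when clinically indicated. Participants are trained to recognise symptoms, the withdrawal criteria apply throughout (Sections 2.5.1 and 7.1), and three orthostatic discontinuations trigger a DSMB review (Section 9.5). Adaptation is not a listed objective or endpoint in Section 3. The 5 mg and 10 mg arms are not titrated, so they give readings from Day 1 to Week 2 at constant dose against concurrent placebo.

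Most of this stands, and it rules out three stronger readings.

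- A reader might infer that orthostatic findings must decline with time on drug because of the schedule. Outside the Intensive PK subset, Day 1 and Week 2 have the same number of readings. After Week 2 a by-visit table of scheduled data would be empty, not falling.
- A reader might infer that nobody looks after Week 2. Symptomatic events are still sought and acted on. What is mainly lost is the fall without marked symptoms.
- A reader might take the protocol to promise an assessment of adaptation specifically at 20 mg. Section 4.2 ties the aim to the escalation in that arm and does not specify the dose.

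The phase 1 rationale does not close the gap. The repeat-dose data come from healthy adults aged 18 to 45, in cohorts of 8, over 5 days plus one further dose. In the 15 and 30 mg single-dose groups, vital signs were not taken when the postural events occurred. Section 2.2.1.2 reports one orthostatic event at hour 8 in a study with doses up to 15 mg. This trial treats patients for 12 weeks with no upper age limit.

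A Week 12 reading has a weakness of its own. Participants with severe orthostatic symptoms will have been withdrawn, and Section 9.1 assumes 20% dropout. A crude comparison of Day 1 with Week 12 could therefore show apparent adaptation through selection.

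**Conclusion.** The point holds as a gap in scheduled measurement. Week 2 is the only scheduled orthostatic visit certain to be at 20 mg, and 69 to 70 of the 77 days at that dose (about 90%; 87% to 94% across the visit window) follow it. Over that time, persistence or loss of orthostatic effect shows only through symptoms, adverse event reports or clinically indicated checks. The 90% is time elapsed after the last scheduled check, not a count of days without a reading.

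This limits the adaptation aim in Section 4.2. It does not defeat it, because the 5 mg and 10 mg arms support an early comparison at fixed dose. Nor does it show that late safety data will be misreported, since no late orthostatic conclusion is planned. The change is a worthwhile low-cost improvement.

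The result assumes the planned titration without interruption (Section 7.1.2 requires re-titration in the 20 mg arm after a break) and the visit windows and day numbering stated above.

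**What to change.** **Schedule of Activities and Section 8.4.2.** At Week 12, add sitting and standing BP and heart rate predose and 1 hour after the in-clinic dose, alongside the existing prolactin samples. Section 6.4 omits Week 12 from its list of visits with dosing at the site and should be aligned with Sections 1.3, 6.1 and 8.8.

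**SAP.** Section 9.3 leaves it to be finalised before unblinding, so the following can still be specified:

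- Summarise the 1-hour orthostatic change from predose, that is (standing − sitting at 1 h) − (standing − sitting predose), at Day 1, Week 1, Week 2 and Week 12. Show it by arm, including placebo, and by actual dose at the visit.
- Base any statement on change over time on this common 1-hour reading, in participants measured at both visits being compared.
- Report beside it, by arm, how many participants left earlier because of orthostatic events.
- Record the time of the previous dose. The clinic dose at Weeks 1 and 12 need not be the first of the day, so the predose value may carry some residual effect.

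**Reconcile Week 1.** Section 2.5.1 describes 2 hours of observation with hourly orthostatic BP at that visit, while Section 8.4.2 schedules a reading at 1 hour only. The two passages must be made to agree.

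**Cost.** Three extra readings per participant if the routine sitting set is taken predose, otherwise four, at a visit where the participant is already dosed and kept for 1 hour, plus one SAP table. The remaining limit is that Week 12 data come only from participants still on treatment. Matching participants and reporting departures makes that selection visible but does not remove it.
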